7. STUDY POPULATION

Data are summarized for the safety population (Section 6.3.2).

7.1. Screen Failures

Screen failures are not summarized.

7.2. Subjects Disposition

A disposition summary includes the number and percentage of patients in the following categories:

- Patients with prior participation in LARIAT
- Patients with prior participation in CATALYST and randomized to placebo (only summarized when unbinding of CATALYST has occurred)
- Patients with prior participation in CATALYST and randomized to bardoxolone methyl (only summarized when unblinding of CATALYST has occurred)
- Continuing (or complete) treatment
- Terminate from the study
 - Reason for terminating study

Results will be summarized by analysis population (Section 6.3). A listing of disposition is provided for all enrolled patients.

7.3. Demographic and Baseline Characteristics

Summaries of demographic and other baseline characteristics summaries are presented by treatment analysis group (Section 4.5) for all analysis populations. Derivation of demographic and other baseline characteristics are described in Section 6.5.

Demographic and other baseline characteristics include the following:

- Age (years) at the date of informed consent
- Sex: female; male
- Race
- Ethnicity: Non-Hispanic/Latino; Hispanic/Latino
- Weight, body mass index (BMI)
- Geographic location: US; Other
- Baseline disease characteristics (WHO functional class, baseline 6MWT)
- Connective tissue disease (CTD) etiology (none, scleroderma, lupus, mixed, and other)
- Number of background medications

- Background medication class (endothelin receptor antagonist, phosphodiesterase type-5 inhibitors, soluble guanylate cyclase, prostacyclins)
 - Background medications (e.g., ambrisentan, bosentan, riociguat, etc.)

7.4. Listing of Subject Inclusion and Exclusion Criteria

A listing of enrolled patients who did not meet inclusion or exclusion criteria is generated.

7.5. Medical History and Medical Conditions Present at Entry

Medical history is summarized by treatment analysis group (Section 4.5, as well as all patients combined). For patients participating in CATALYST or LARIAT, medical history values are the values recorded at the CATALYST or LARIAT Screening visit. Medical history is coded using MedDRA (Medical Dictionary for Regulatory Activities) version 19.0. Medical history items are summarized by MedDRA SOC and PT. Patient listings are also provided.

8. EFFICACY

Analyses of 6MWT, Borg dyspnea scale include only summary statistics by visit window (Section 6.5.5) Summary statistics for observed values and change from baseline are presented.

8.1. 6-Minute Walk Test

The change from baseline in 6MWT score is summarized by visit and treatment analysis group (Section 4.5). Summary statistics for observed values and change from baseline are presented by visit window (Section 6.5.5). Line plots of change from baseline of 6MWT by visit and treatment analysis group (including overall patients) are generated up to and including study Week 120.

8.2. Borg Dyspnea Index

The change in Dyspnea scale is summarized by visit and treatment analysis group (Section 4.5). Summary statistics for observed values and change from baseline are presented by visit window (Section 6.5.5).

8.3. WHO/ NYHA Functional Class Assessment

WHO functional class assessment values collected at each visit using the appropriate analysis windows (Section 6.5.5) will be used. The number of patients in each class Section 12.2) is summarized at each analysis visit by treatment analysis group (Section 4.5). The categorical summaries for shift from baseline to highest and lowest WHO/ NYHA Functional Class are presented. The shift from baseline values includes WHO/ NYHA Functional Class I, II, III, IV and a category for missing data.

9. SAFETY AND TOLERABILITY

Safety data (including AEs, vital signs, BNP, and NT-proBNP) are listed and summarized for patients in the safety population (Section 6.3.2) by treatment analysis group (Section 4.5).

The analysis visit windows (Section 6.5.5) are used for all safety analyses. Any results not included in summaries based on analysis visit window definitions are presented in data listings.

9.1. Adverse Event Preferred Term and Body/Organ System Summary Tables

AEs are summarized by treatment analysis group as defined by the safety analysis set. General considerations for AE summaries and calculations are:

- Multiple events by preferred term (PT) and system organ class (SOC) are counted once only per patient for each treatment analysis group.
- For summaries by severity, only the most severe event is counted per patient for each treatment analysis group.
- For summaries by relationship, for frequency counts by patient, only the most related event is counted per patient for each treatment analysis group.
- An AE with a missing resolution date or incomplete date that is not identified as continuing is assumed to be continuing and no duration is calculated.
- Only treatment-emergent adverse events (TEAEs) are included in summaries.

AEs are coded using MedDRA (Medical Dictionary for Regulatory Activities) version 19.0. In MedDRA, each verbatim term is mapped to a preferred term and high level term (HLT), which is then mapped to a system organ class. Tables and listings present data at the SOC and PT level.

Treatment-emergent adverse events (TEAEs) are events that either:

- Had a date of onset on or after the date of the date of first dose in the RANGER study and not more than 30 days after the date of the last dose of study drug in the RANGER study, or
- Had no recorded date of onset with a stop date after the first dose of study drug, or
- Had no recorded date of onset or stop date.

Adverse events with a date of onset in LARIAT or CATALYST that continued during the RANGER study are not considered TEAEs.

In addition, adverse events which occurred >30 days after the date of last dose of study drug are listed as late-onset AEs (LOAEs). These are adverse events that had a date of onset more than 30 day after the date of the last dose of study drug.

The investigator grades the severity of the AEs as mild, moderate, or severe as defined in the study protocol Section 11.5.

Association or relatedness to the study medication are graded by the investigator according to criteria specified in Section 11.4 of the study protocol.

As defined in the protocol and captured on the CRF, a serious adverse event (SAE) is an adverse event that results in any of the following:

- Death;
- A life-threatening adverse drug experience;
- Inpatient hospitalization or prolongation of existing hospitalization;
- Results in persistent or significant incapacity or substantial disruption of the ability to conduct normal life functions;
- Results in a congenital anomaly or birth defect in an offspring of a patient taking study drug;
- Is an important medical event.

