### **11.2. Adverse and Serious Adverse Events**

#### **11.2.1. Definition of Adverse Events**

##### **11.2.1.1. Adverse Event**

An AE is defined as any untoward medical occurrence in a patient regardless of its causal relationship to study drug. An AE can be any unfavorable and unintended sign (including any clinically significant abnormal laboratory test result), symptom, or disease temporally associated with the use of the study drug, whether or not it is considered to be study-drug related. Included in this definition are any newly-occurring events or previous condition that has increased in severity or frequency since the administration of study drug.

All AEs that are observed or reported by the patient during the study (from time of administration of the first dose at the Day 1 visit until the final visit indicated in [Table 3](#)) must be reported, regardless of their relationship to study drug or their clinical significance.

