#### **11.6. Recording Adverse Events**

All conditions present prior to the administration of the first dose of study drug (Day 1) in a previous study with bardoxolone methyl should be documented as medical history in a previous study with bardoxolone methyl. After the first dose, documentation of AEs shall continue until 30 days following administration of the final dose of study medication under this protocol (*i.e.*, through the End-of-Treatment visit), regardless of the relationship of the AE to study drug. Information to be collected will include type of event, date of onset, date of resolution, investigator-specified assessment of severity and relationship to study drug, seriousness, as well as any action taken.

While an AE is ongoing, changes in the severity (*e.g.*, worsening and improving) should be noted in the source documents, but when documenting the AE, only the total duration and greatest severity should be recorded in the eCRF. AEs characterized as intermittent will require documentation of onset and duration.

All drug-related (possibly, probably, or definitely related, see [Section 11.4](#)) AEs and abnormal laboratory test results reported or observed during the study must be followed to resolution (either return to baseline or within normal limits). All other AEs will be followed through the final visit indicated in [Table 3](#), as appropriate.

AEs resulting from concurrent illnesses, reactions to concurrent illnesses, reactions to concurrent medications, or progression of disease states must also be reported. Preexisting conditions (present before the start of the AE collection period) will be considered concurrent medical conditions and should NOT be recorded as AEs. However, if the patient experiences a worsening or complication of such a concurrent condition, the worsening or complication shall be recorded as an AE. Investigators shall ensure that the AE term recorded captures the change in the condition (*e.g.*, “worsening of...”). Any improvement in condition shall be documented per [Section 9.10.7](#).

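### The TEAE definition has no worsening or seriousness criterion, so a parent-study AE kept as one record that deteriorates on RANGER drug is missing from every AE summary table

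*SAP*

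**What the plan says.** **SAP 9.1** gives three routes to TEAE status. The first, for events with a recorded onset, is "Had a date of onset on or after the date of the date of first dose in the RANGER study", up to 30 days after the last dose. The second is "Had no recorded date of onset with a stop date after the first dose of study drug". The third is "Had no recorded date of onset or stop date". SAP 6.6.3 gives the same three. Section 9.1 then adds "Adverse events with a date of onset in LARIAT or CATALYST that continued during the RANGER study are not considered TEAEs", with no exception, and "Only treatment-emergent adverse events (TEAEs) are included in summaries". The six tables listed in SAP 9.1.2 (all, related, by severity, serious, related serious, leading to permanent discontinuation) all carry that limit. The listings in 9.1.2 do not.

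**Protocol 11.2.1.1** includes in its AE definition a "previous condition that has increased in severity or frequency since the administration of study drug". It starts AE reporting at the first dose on RANGER Day 1.

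**Protocol 11.6** contains two recording rules. For an AE that is ongoing, changes in severity go into the source documents, and "only the total duration and greatest severity should be recorded in the eCRF". For a condition already present when AE collection begins, a worsening or complication is itself to be entered as an AE, with a term that conveys the change.

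**Primary safety endpoint** (Protocol 6.2, SAP 3.2.1): frequency, intensity and relationship of AEs and SAEs, with no restriction to new onset. If the two documents disagree on the planned analyses, SAP section 2 gives the SAP precedence.

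**The concern.** Patients roll over directly from a parent study, so some will bring an ongoing AE into RANGER. CATALYST placebo patients then take bardoxolone methyl for the first time. CATALYST bardoxolone patients restart at Week 28 after completing treatment at Week 24. An event that was mild before Day 1 and became severe or serious afterwards is information that a long-term safety study should count. Under the SAP it may be absent from the frequency, severity, SAE and discontinuation tables, which would bias the primary safety summaries downward.

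Three features of the protocol give those tables weight:

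- Section 5.2.2 reports that the excess fluid-overload risk in the earlier Phase 3 trial fell in the first three to four weeks of treatment.
- Section 11.7 exempts edema and similar common events from routine individual expedited reporting and relies on aggregate review.
- Section 13.1 provides no data safety monitoring committee.

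**Working it through.** The plan states no figure to reproduce. The check applies the SAP 9.1 rule to test records and then asks which kind of record the protocol produces.

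**Step 1. The rule applied.** Take first dose = Day 1 and, for illustration, last dose = Day 400, so the onset window is Day 1 to Day 400 + 30 = 430.

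| Case | Record | Test | Result |
|---|---|---|---|
| 1 | New onset Day 50 | 1 ≤ 50 ≤ 430 | TEAE |
| 2 | Parent-study onset Day −40, mild to severe on Day 20, one record | −40 < 1 | Not TEAE |
| 3 | Parent-study onset Day −40, becomes serious on Day 20, one record | −40 < 1 | Not TEAE |
| 4 | Clinical course of case 2, worsening entered as a new AE with onset Day 20 | 1 ≤ 20 ≤ 430 | TEAE |
| 5 | Parent-study event, onset not recorded, stop Day 60 | 60 > 1 | TEAE |
| 6 | Neither date recorded | default | TEAE |

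Cases 2 and 3 fail on the onset criterion alone, and the exclusion sentence gives the same answer. Deleting that sentence would therefore not cure the problem. Case 3 is missing from the SAE table. A one-record event that turns fatal or leads to discontinuation is lost in the same way. Cases 2 and 4 are the same clinical course with opposite counts. Case 6 counts with no dates at all, while the worsening in case 2 does not count.

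**Step 2. Which record the protocol produces.**

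- *Toward one record (cases 2 and 3).* Protocol 11.6 sets the medical-history cut at the first dose in the previous study and continues: "After the first dose, documentation of AEs shall continue until 30 days following administration of the final dose of study medication under this protocol". SAP 7.5 likewise takes medical history from the parent Screening visit. An AE that began during the parent study is then an ongoing AE and falls under the one-record, greatest-severity rule. The SAP exclusion sentence itself presupposes such records.
- *Toward a new record (case 4).* Protocol 11.2.1.1 starts AE reporting at the first RANGER dose. A parent-study AE ongoing on Day 1 then predates collection, and its worsening is a separate AE under 11.6. Section 9.10.7 points the same way for examination findings: significant Day 1 findings go to medical history, and later changes that qualify as AEs are entered as AEs.

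No sentence says which rule governs an AE that spans the rollover.

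**Step 3. Size.** Patients missing a TEAE = N × p × w × s, where p is the share entering with an ongoing parent-study AE, w the share of those whose event deteriorates, and s the share of those kept as one record. SAP 4.3 gives a maximum N of 200 + 166 = 366. The documents give none of p, w or s. Assume p from 10% to 50% and w from 2% to 20%:

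- s = 1, low: 366 × 0.10 × 0.02 = 0.7 patients (0.2 percentage points)
- s = 1, high: 366 × 0.50 × 0.20 = 36.6 patients (10 percentage points)
- s = 0: no patients

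One patient is 100/366 = 0.27 percentage points. These figures show scale only; they are not an estimate.

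**The case against.** The strongest defence is that the plan works as written. AE reporting in RANGER begins at the first dose on Day 1, so a parent-study AE still present then is a pre-existing condition. Protocol 11.6 sends its worsening to a new AE, and 9.10.7 does the same for examination findings such as edema. On that reading the SAP exclusion removes only events that merely carried on, and worsening is counted through its own record. In addition, the listings of all AEs, SAEs and discontinuation AEs are not limited to TEAEs, and weight, BNP and NT-proBNP are summarized whatever the AE onset. All analyses are descriptive.

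Much of this stands. It shows that the loss is conditional, and it rules out the inference that AE collection, for the purpose of the 11.6 worsening rule, began before the parent study; 11.2.1.1 says otherwise. A reader might also infer that TEAE status rests on onset date alone, or that every parent-study AE is excluded. Neither is right, because cases 5 and 6 are classified without an onset date and count.

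The defence does not remove the one-record instruction, which sits in the same section and fits an AE that is ongoing at rollover. Nor does it supply a rule in the SAP for the record that results. Listings do not replace the incidence, severity and SAE tables that report the primary endpoint.

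A practical objection also has force. The SAP is dated 5 June 2020, after termination on 30 March 2020, so a new recording instruction to sites cannot act prospectively. Because the eCRF is to carry only the greatest severity, some dates of worsening would have to come from source notes at up to about 150 centers.

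**Conclusion.** The TEAE rule needs changing. The protocol text supports two recording practices, and the SAP undercounts under one of them. A parent-study AE held as one record that worsens, becomes serious, turns fatal or leads to discontinuation after the first RANGER dose enters no AE summary table. That conflicts with the protocol's own definition of an AE, and the SAP takes precedence for the analyses. Any bias in the summary tables from this source is downward.

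It would go too far to say that such events are certainly lost. If every site entered worsening as a new AE, none would be. The number affected cannot be derived from the documents, and the span of 0 to about 37 patients rests wholly on assumed rates and on the maximum enrollment of 366. The conclusion itself depends only on the SAP wording and on at least some sites having followed the one-record rule.

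**What to change.** 1. **SAP 6.6.3 and 9.1.** Add a criterion: an AE with onset before the first RANGER dose is treatment-emergent if it increased in severity, became serious or led to permanent discontinuation of study drug on or after that dose and within 30 days of the last dose. Limit the exclusion sentence to parent-onset AEs that did none of these.
2. **Protocol 11.6.** Reconcile the one-record rule and the worsening rule with 11.2.1.1 and 9.10.7 for AEs that span the rollover. Because the study has been terminated, give effect to this through the SAP.
3. **Data.** Use the seriousness, action-taken and severity fields already in the eCRF to identify candidate events. Then run a limited query of AEs ongoing at Day 1 to date the change; 11.6 requires severity changes to be noted in source documents.
4. **Minimum alternative.** Leave the TEAE definition as it is and add a separate table, by treatment analysis group, of parent-onset AEs that worsened, became serious or led to discontinuation in RANGER.

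The cost is one SAP criterion, one narrowed sentence, some source-data queries and slightly higher TEAE counts. The queries are the main burden, and restricting them to AEs ongoing at Day 1 keeps them limited.

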9.1.1. Missing and Partial AE Onset Dates

Rules for handling missing partial AE Onset Dates are included in Section [6.6.3](#).

9.1.2. Summaries of Adverse Events for Serious Adverse Events (SAE), Adverse Event Dropouts, and Death

Treatment-emergent AEs are summarized by treatment analysis group at onset of the AEs. For each treatment analysis group, SOC, and PT, the number and percentage of patients reporting an event are calculated. For subgroups, the number and percentage of patients reporting an event within a subgroup are calculated. In summary tables, SOC are presented alphabetically and events within SOC are presented by decreasing frequency count.

Summary tables (number and percentage of patients) of AEs (by SOC and PT) are provided by treatment analysis group as follows:

- All treatment-emergent AEs
- All treatment-emergent related AEs (definitely, probably, or possibly related)
- All treatment-emergent AEs by severity
- All treatment-emergent serious adverse events (including deaths)
- All related treatment-emergent serious adverse events (including deaths)
- All treatment-emergent adverse events leading to permanent discontinuation of study drug.

Listings are provided showing:

- All AEs
- Serious adverse events (including deaths)
- AEs leading to discontinuation of study drug.

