## **12. STATISTICS**

### **12.1. Sample Size**

The aim of this long-term extended access study is primarily to provide continuing treatment to patients with bardoxolone methyl and to assess long-term safety and tolerability, hence no single primary variable has been identified. Patient numbers will be determined by those who have been treatment-compliant and who have previously participated in clinical studies with bardoxolone methyl.

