3.2. Study Endpoints

3.2.1. Primary Safety Endpoints:

Frequency, intensity, and relationship to study drug of adverse events (AEs) and serious adverse events (SAEs) and change from baseline in the following assessments: physical examinations, vital sign measurements, BNP, N-terminal pro-brain natriuretic peptide (NT-proBNP), and weight.

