6.2. General Post Text Summary Table and Individual Subject Data Listing Format Considerations

Unless otherwise specified, descriptive statistics for continuous variables include the number of patients with data (N), mean, standard deviation (SD), median, minimum, and maximum. The same number of decimal places as in the observed value are presented when reporting minimum and maximum; 1 more decimal place than in the observed value is generally presented when reporting mean; and 2 more decimal places than in the observed value are presented when reporting SD. When calculating the minimum and maximum of average baseline values, the same number of decimal places as in the observed value will be presented when reporting minimum and maximum. For imputed values and the average of baseline values, the average values will be rounded to the same number of decimal places as the source value.

Categorical (qualitative) data are presented using frequency counts and percentages. All percentages are rounded to 1 decimal place, unless otherwise specified. Percentages equal to 100 are presented as 100% and no percentages are presented for zero frequencies. Where individual variable values are missing, summaries of categorical data are based on reduced denominators (i.e., only patients with available data are included in the denominators). For summaries of AEs and concomitant medications, the percentages are based on the number of patients who received study drug within each summary group.

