6.6.3. Missing Start and Stop Dates for Adverse Events

Treatment-emergent adverse events (TEAEs) are events that either:

- Had a date of onset on or after the date of the date of first dose of study drug and not more than 30 days after the date of the last dose of study drug, or
- Had no recorded date of onset with a stop date after the first dose of study drug, or
- Had no recorded date of onset or stop date.

Adverse events with incomplete start dates are considered after the date of first dose if:

- Day and month are missing, and the year is equal to or after the year of the first date of study drug administration;
- Day is missing and the year is after the year of the first date of study drug administration;
- Day is missing and the year is equal to the year of the first date of study drug administration and the month is equal to or after the month of the first date of study drug administration; or
- Year is missing.

Adverse events with incomplete start dates are considered on or within 30 days of last dose, if:

- Day and month are missing, and the year is equal to or before the year of the date of last dose of study drug plus 30 days;
- Day is missing and the year is equal to or before the year of the date of last dose of study drug plus 30 days, and month is equal to or before the month of the date of last dose of study drug plus 30 days;
- Year is missing.

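### Adverse event frequency is tabulated only as crude patient percentages over unequal follow-up; a rate per 100 patient-years should stand beside them

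*SAP*

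**What the plan says.** SAP 3.2.1 opens the primary safety endpoints with "Frequency, intensity, and relationship to study drug of adverse events (AEs) and serious adverse events (SAEs" and continues with changes from baseline in other assessments. AE frequency is therefore one component among several, and Protocol 12.1 states that "no single primary variable has been identified".

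SAP 9.1.2 plans six AE tables: all treatment-emergent AEs (TEAEs), related, by severity, serious, related serious, and leading to discontinuation. All give one statistic: "For each treatment analysis group, SOC, and PT, the number and percentage of patients reporting an event are calculated". For the denominator, SAP 6.2 says "the percentages are based on the number of patients who received study drug within each summary group". Under SAP 9.1, repeat events are "counted once only per patient for each treatment analysis group". The window opens at the first RANGER dose and takes in onsets "not more than 30 days after the date of the last dose of study drug in the RANGER study".

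Follow-up has no common length. LARIAT and CATALYST patients enter at different points (SAP 4.1), treatment is open-ended, and the study was terminated on 30 March 2020 (SAP 6.6.4).

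The SAP does carry related information:
- Exposure duration, and patients on drug by visit and dose (SAP 9.2).
- Days since first or last dose, in AE listings (SAP 6.5.3).
- Weight, vital signs, BNP and NT-proBNP by analysis visit, including Weeks 1, 2, 4, 6 and 8 (SAP 6.5.5, 9.4, 9.5).

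**The concern.** The study exists to describe long-term safety. A percentage that pools patients followed for a few months with patients followed for years is not a frequency per unit of time, and it cannot readily be set beside figures from studies of other lengths. After CATALYST is unblinded, the PBO → BARD and BARD → BARD columns will also stand side by side. Readers will compare them even though the SAP plans no comparison.

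Timing matters too. For former placebo patients RANGER Day 1 starts their first exposure to the drug. Protocol 9.1.1 singles out the first 8 weeks for daily home weights, but no AE or SAE table separates that period from the rest.

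**Working it through.** **Does any other sentence supply a time base?** SAP 9 says the visit windows apply to all safety analyses. But the table list in 9.1.2 has no visit or period dimension, and SAP 6.5.5 defines the windows for choosing the assessment nearest a target day. The reference in 9.1.2 to the group at onset of the AE names a group, not a period. Groups are fixed by prior study and treatment (SAP 4.5). So no time base is planned.

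**The plan's own figure.** 200 (CATALYST) + 166 (LARIAT) = 366, as in SAP 4.3. The documents give no AE rate and no exposure by group, so everything below is illustration under stated assumptions.

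**1. Same hazard, different follow-up.** With constant hazard r, the expected percentage at time t is p(t) = 1 − exp(−rt). Assume BARD → BARD holds 100 CATALYST patients (half of the maximum 200) and 166 LARIAT patients followed for 2 years. Assume all CATALYST patients, including PBO → BARD, are followed for time c. The ratio of crude percentages is [(100·p(c) + 166·p(2))/266] / p(c).

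| r per year | p(0.5) | p(1) | p(2) | ratio, c = 1 y | ratio, c = 0.5 y |
|---|---|---|---|---|---|
| 0.1 | 0.049 | 0.095 | 0.181 | 0.149/0.095 = 1.6 | 0.131/0.049 = 2.7 |
| 0.3 | 0.139 | 0.259 | 0.451 | 0.379/0.259 = 1.5 | 0.334/0.139 = 2.4 |
| 1.0 | 0.393 | 0.632 | 0.865 | 0.777/0.632 = 1.2 | 0.688/0.393 = 1.7 |

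With equal exposure every ratio is 1.0.

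**2. What a reader can recover from the planned tables.** Take −ln(1 − p)/T, with p the crude proportion and T the mean exposure. If everyone has the same exposure this returns r exactly. Now spread exposure uniformly over 0 to 2.75 years (1 July 2017, an assumed day in the month the protocol estimates for first enrolment in Germany, to 30 March 2020: 1003/365.25 = 2.75). Then p = 1 − (1 − exp(−2.75r))/(2.75r) = 0.126, 0.319, 0.660, and T = 1.375. The results are 0.098, 0.280 and 0.784, or about 2%, 7% and 22% low for r = 0.1, 0.3 and 1.0. The simpler n/(N × mean duration) does worse: 9%, 25% and 57% low even when everyone has 2 years.

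**3. A short early excess.** Assume background hazard h = 0.15 per year, multiplied by k until week e and then back to h. The first-event rate is events divided by person-time at risk, here divided by h. Example with k = 3, e = 4, over 8 weeks:
- Survival at 4 weeks is exp(−0.45 × 0.0767) = 0.9661, and at 8 weeks 0.9661 × exp(−0.15 × 0.0767) = 0.9550.
- Events = 0.0450. Person-time = 0.0339/0.45 + 0.9661 × 0.01144/0.15 = 0.149 years.
- 0.0450/0.149/0.15 = 2.0.

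| Follow-up | Rate ratio, k = 3 or 5 and e = 3 or 4 weeks |
|---|---|
| first 8 weeks | 1.8 to 3.0 |
| 0.5 y | 1.24 to 1.65 |
| 1 y | 1.12 to 1.34 |
| 2 y | 1.07 to 1.18 |

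The 8-week cut itself dilutes an excess that ends at 3 to 4 weeks, but much less than the whole period does.

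**4. Contact density.** Protocol Table 3 schedules ten contacts after Day 1 up to Day 56 (Days 3, 7, 10, 14, 21, 28, 31, 38, 42, 56). From Week 24 there is one per 24 × 7 = 168 days. (10/56)/(1/168) = 30.

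**5. End of exposure.** SAP 9.2 takes the last kit date as last dose for patients still on treatment at an interim or final cut. SAP 6.6.4 imputes a missing treatment end date as 30 March 2020. With 24-weekly dispensing the two can differ by up to about 168 days per patient.

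**The case against.** The strongest reply is that the SAP does what Protocol 12.3 asks, which is counts and percentages for categorical data, and that neither document defines frequency per unit of time. The study is descriptive, unpowered and without planned comparisons. Exposure and patients on drug by visit are tabulated, so a reader can approximate a rate. The early fluid concern is covered by weight, vital signs, BNP and NT-proBNP at Weeks 1 to 8. Protocol 5.2.2 also says the fluid-overload risk seen in late-stage chronic kidney disease has not been observed in pulmonary arterial hypertension patients.

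All of this stands, and it is why the point is an improvement and not a fault. It does not remove the gap. The approximation is good for rare terms and weaker for common ones, and it gives no onset timing. By-visit laboratory values are not AE counts.

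A reader might go further and infer that the group columns are biased in a known direction. The documents do not support that, because they do not give exposure by group and equal exposure gives a ratio of 1.0. A reader might also infer that the planned tables hide any early excess. That goes too far: at 0.5 to 1 year of follow-up a whole-period rate ratio of 1.12 to 1.65 remains in the illustration, and listings show onset day.

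An objection to the onset-period table also stands. With contacts about 30 times denser early on, a non-serious excess could be ascertainment alone. The added monitoring came only with Amendment 2 in July 2018 (SAP 2), so patients enrolled before it may have been observed differently.

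**Conclusion.** The point holds as a worthwhile, inexpensive addition. One component of the primary safety endpoint is reported without a time base although follow-up is unequal by design. The planned tables are valid for what they state, follow the protocol and need not be replaced.

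The actual effect cannot be sized from the documents. The between-group ratios of about 1.2 to 2.7 rest on constant, equal hazards and assumed follow-up. The 2%, 7% and 22% recovery errors rest on uniform exposure up to 2.75 years. The early-excess figures rest on an assumed 3- to 5-fold excess over a background of 0.15 per year. The onset-period table is secondary and optional.

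**What to change.** **Main change, SAP 9.1.2.** Beside n (%), give patients with a first event per 100 patient-years at risk for TEAEs, related TEAEs, SAEs and TEAEs leading to discontinuation, by treatment analysis group and overall.
- Person-time starts at first RANGER dose. It ends at the earliest of first event, last dose + 30 days, death, last contact or, at an interim, the data cut. This matches the TEAE window.
- At final lock use the recorded last dose date, and apply SAP 6.6.4 if it is missing. Limit the last-kit rule in SAP 9.2 to interim cuts.
- Keep SAP 6.6.3 for TEAE status. It admits events under "Adverse events with incomplete start dates are considered after the date of first dose if", and SAP 9.1 admits those that "Had no recorded date of onset or stop date". For the rate, date such events at the earliest day the recorded parts allow, not before first dose, and report how many patients this affects.

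**Optional.** Add one SAE and one TEAE table by onset at ≤8 and >8 weeks from first RANGER dose, with patients and patient-years at risk per period and a row for unknown onset. Show PBO → BARD separately, and split BARD → BARD by LARIAT and CATALYST origin, because entry points differ. Footnote the contact density and the Amendment 2 change, and say that the SAE table is the more interpretable.

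**Cost.** Extra columns, up to two tables and one clarified rule, all from dates already collected. The price is more output, an assumption of roughly constant hazard within each period, and the ascertainment caveat. Results stay descriptive.
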